Low risk patients will be assigned to Arm 2 where they will be treated with de-intensified RT: 42 Gy (vs 60 Gy) and no cisplatin at all. Reduction in treatment-related toxicity is expected in Arm 2.

High risk patients will be assigned to Arm 3 where they will be treated with standard intensive therapy, so reduction in treatment-related toxicity is not expected in this group.

Mucosal damage is the key mediator of most of the acute toxicity for POART and POACRT. The primary endpoint for the **MINT** trial is weight loss, a reliable, easily measured and practical surrogate marker of mucosal toxicity. **Historical data showed that the percent weight loss during POACRT in patients with HPV-related OPSCC was 7.39%. The primary hypothesis of this trial is that the percent weight loss of patients in Arm 1 during POAmCRT will be 3.7% (50% reduction).**

Secondary endpoints of mucosal toxicity to be determined include the proportion of patients who had PEG tubes placed, who experienced a doubling of the serum creatinine from baseline (a surrogate of dehydration and/or cisplatin toxicity), and who remained on narcotics at 6 weeks after POAmCRT. The secondary hypothesis for this trial is the proportion of patients with the composite endpoint of PEG tube placement/doubling of the serum creatinine/requirement for narcotics at 6 weeks after POAmCRT will be reduced from the historical control of 72.6% to 36.3% (50% reduction). Similar endpoints will be monitored for Arm 2, although the number of patients in this arm is expected to be small based on historical data. As such, we will not develop formal hypothesis testing for Arm 2, but will report the toxicity data in descriptive form.

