2.2 Secondary Objectives

1. To evaluate the narcotics administration of patients 6 weeks after POAmCRT (Arm 1).
2. To determine the disease recurrence rate at 24 months post-treatment in each arm.

3. To determine progression free survival (PFS) and overall survival (OS) for each arm.
4. To evaluate the proportion of PEG tube placements in each arm.
5. To determine the serum creatinine changes in patients receiving POAmCRT (Arm 1).

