5.6.1 Six Week (+/- 1 week) Assessment

1. Physical examination and weight (kg).
2. Serum creatinine (BMP).
3. Documentation of ECOG performance status.
4. Documentation of narcotic and PEG tube usage.
5. Documentation of patient symptoms using NCI-CTCAE version 4.0.
6. Completion of QOL questionnaires
7. CT Neck.
8. OPTIONAL: Speech and swallowing assessment

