5.7 Evaluations for Toxicity and Disease Relapse

All patients who receive any study treatment (starting point of “study treatment” is first dose of post-operative RT) are evaluable for toxicity. Patients are evaluated from first day of study treatment until five years after the conclusion of treatment, or death.

All patients who undergo surgery are evaluable for disease relapse.

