10.4.4 Endpoint Analysis

The primary endpoint is percent weight loss. Weight (kg) will be collected weekly during radiation within each arm. The percent weight loss from the baseline is calculated at any post-baseline. The generalized estimating equation (GEE) model with identity link function will be used to analyze this percent weight loss data, in which the correlation among the repeated measures from the same patient need be considered. The autoregressive

of first order as working correlation structure will be used. The GEE model includes baseline weight and time points. The p-value is estimated to assess whether the percentages of weight loss across all time points are different. Least square means for percent weight loss at each time point and mean differences between any time points will be estimated, and their standard errors will be calculated within the use of GEE sandwich method when accounting for within-patient correlation.

The secondary endpoints include proportion of PEG tube placements for all enrolled patients, the serum creatinine changes in patients receiving POAmCRT, proportion of the narcotics administration of patients 6 weeks after POAmCRT, and RFS. Proportions of PEG tube placements for all enrolled patients and the narcotics administration of patients 6 weeks after POAmCRT and their associated 95% confidence intervals will be calculated assuming a binomial distribution²³. The serum creatinine is measured at the baseline and six weeks after POAmCRT. The paired t-test will be considered to test the change.

Disease recurrence rate at 24 months post-treatment (DRR-24) in each arm is calculated for each arm. The proportion and 95% CI from binomial distribution will be shown for Arm 1. If 95% upper CI is smaller than 20%, then the risk of disease recurrence is deemed as acceptable. If 95% lower CI is larger than 20%, then the risk of disease recurrence is deemed as unacceptable. Given our small sample size, there are some uncertainties. Therefore, we do not test the hypothesis about (DRR-24) but provide a preliminary data for planning future studies.

PFS will be calculated from the date of surgery to the date of progression, death of any cause, or last known date alive. OS will be calculated from the date of surgery to the date of death or last known date alive. PFS and OS will be evaluated using Kaplan Myer.

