11.0 DATA SUBMISSION SCHEDULE

Case report forms with appropriate source documentation will be completed according to the schedule listed in this section.

Case Report Form	Submission Schedule
Original Consent Form	Prior to registration
On-Study Form	Prior to starting treatment
Surgery Form	Time of surgery
QOLs Forms	Baseline Interim assessment Day 1 of RT (-7/+0) Day 22 after start of RT (Arm 1 & 2 +/- 2 days; Arm 3 +/- 5 days) Day 36 after start of RT (Arm 1 & 2 +/- 2 days; Arm 3 +/- 5 days) 6 weeks after completion of adjuvant therapy 4 months after completion of adjuvant therapy 6 months after completion of adjuvant therapy 12 months after completion of adjuvant therapy 24 months after completion of adjuvant therapy
Toxicity Form	Continuous
Weight Form	Baseline, weekly during treatment, and at each follow-up visit
Treatment Summary Form	Completion of treatment
Follow Up Form Narcotics Form PEG Form	6 weeks, 4 months, 6 months, 12 months, 18 months, 24 months, 30 months, 36 months, and 48 months after the completion of adjuvant therapy
RECIST Form	Baseline, 6 weeks after completion of adjuvant therapy, and 6 months after completion of adjuvant therapy

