14.0 STUDY CALENDARS

14.1 Baseline and Treatment Calendar

	Baseline ⁴	Surgery	Interim Assessment (14 to 42 days post-surgery)	Post-operative Adjuvant Chemotherapy/Radiation		
				D1	D2 ¹²	D36 ¹²
Informed consent	X					
Laryngoscopy ¹	X					
PE w/ECOG PS	X		X	X	X	X
Weight	X			X ⁸		X ⁸
Comorbidity index	X		X			
CBC	X		X	X	X	X
CMP + magnesium	X					
BMP + magnesium			X	X	X	X
PT/PTT	X		X			
Pregnancy test ²	X					
Neck CT w/contrast	X					
FDG-PET/CT	X					
QOLs ³	X		X	X ¹³	X	X
OPTIONAL: Speech & Swallow Study ¹⁰	X		X	X ¹¹	X	X ⁹
Surgery ⁵		X ⁵				
Rad Tx Planning			X			
IMRT or IMPT ⁶				X		X ⁹
Arms 1 & 3: Cisplatin ⁷				X ⁷	X ⁹	X ⁹
AE assessment	X		X	X	X	X
Documentation of narcotic usage				X	X	X

1. Assessment of primary tumor site will be done by laryngoscopy performed in the office or operating room.

2. In women of childbearing potential only.

3. FACT H&N, M.D. Anderson Dysphagia Inventory, University of Michigan Xerostomia Index, Scale of Subjective Total Taste Acuity, and Neck Dissection Impairment Index.

4. Baseline assessments must take place no more than 35 days prior to enrollment, with the exception of PET scans (within 42 days).

5. See Section 5.2.

6. Arms 1 and 2: Once daily M-F, with one BID treatment each week for 4200 cGy in 21 fractions. Arm 3: Once daily M-F for 6000 cGy in 30 fractions

7. To be given during initial 5 doses of POART. See Section 5.4.1 for fluids and premedications. On Arm 3, cisplatin will only be given to patients with pathologic evidence of positive margins or ECE (see section 1.9).

8. Collect weight weekly during Radiation.

9. Arm 3 only.

10. Modified barium swallow and the Performance Status Scale for Head and Neck Cancer (PSS-HN) questionnaire.

11. Modified barium swallow NOT needed on this day.

12. Arm 1 & 2 +/- 2 days; Arm 3 +/- 5 days

13. -7/+0 days

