14.2 Follow-up Calendar

	Short Term Follow-up		Long-Term Follow-Up							Annually Thereafter ⁵
			Months post-end of CRT ³							
	6 weeks post-end of tx (+/- 1 week)	4 months post-end of tx (+/- 2 weeks)	6	12	18	24	30	36	48	
PE w/ECOG PS + Weight	X	X	X	X	X	X	X	X	X	X
BMP	X									
Neck CT w/contrast	X		X	X	X	X		X		
Chest CT w/contrast ²			X	X	X	X		X		
QOLs	X	X	X	X		X				
OPTIONAL: Speech & Swallow Assessment		X	X	X ⁴		X ⁴				
Documentation of narcotic usage	X	X	X	X	X	X	X	X	X	
Documentation of PEG tube usage	X	X	X	X	X	X	X	X	X	
AE assessment	X									

1. FACT H&N, M.D. Anderson Dysphagia Inventory, University of Michigan Xerostomia Index, Scale of Subjective Total Taste Acuity, and Neck Dissection Impairment Index.

2. Chest x-ray (PA and Lateral) may be substituted for chest CT if it is unable to be obtained (i.e. insurance issues)

3. +/- 6 week window

4. Modified barium swallow not required

5. For 5 years (total of 10 years of follow-up)

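### The PEG endpoint counts tube placements, but the schedule records only PEG use, first at the 6-week post-treatment visit, with no PEG item before or during radiotherapy

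*Combined protocol and SAP*

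**What the plan says.** **Endpoint.** Secondary objective 4 in Section 2.2 is "To evaluate the proportion of PEG tube placements in each arm". Section 1.9 states: "Secondary endpoints of mucosal toxicity to be determined include the proportion of patients who had PEG tubes placed". Section 10.4.4 gives "Proportions of PEG tube placements for all enrolled patients" a binomial 95% confidence interval. All three describe an event: a tube was placed. Neither Section 2.2 nor 10.4.4 says when counting starts or stops, or what to do with a tube already in place when RT begins.

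**Scheduled data.** The 6-week visit in Section 5.6.1 lists "Documentation of narcotic and PEG tube usage", and Sections 5.6.2 and 5.6.3 repeat the item at later visits. The follow-up calendar (14.2) has a row for "Documentation of PEG tube usage" whose first entry is also the 6-week visit. Section 11 puts the PEG Form on the same schedule as the Narcotics Form: "6 weeks, 4 months, 6 months, 12 months, 18 months, 24 months, 30 months, 36 months, and 48 months" after adjuvant therapy ends.

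**Before and during RT.** The interim assessment (5.3) and the on-treatment procedures (5.4) contain no PEG item. The treatment calendar (14.1) has a row for "Documentation of narcotic usage" at Days 1, 22 and 36, but no PEG row.

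**The concern.** Use at a visit equals cumulative placement only if no tube has been removed by then. Section 1.4 itself calls these tubes temporary. The main period of risk, during RT and the weeks just after, has no scheduled PEG record. The narcotic endpoint, by contrast, is defined at 6 weeks and needs only the 6-week record, yet narcotics are the item recorded during treatment.

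Two errors of opposite sign are possible:

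- A tube placed during RT and removed before the 6-week visit would not be seen, which makes 42 Gy look less toxic.
- A tube placed at or soon after surgery and still in use at 6 weeks would be counted with the RT-related tubes, which makes it look more toxic.

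The PEG proportion is one of the results that would support a claim of reduced toxicity. Placement is also a component of the composite in Section 1.9, which is hypothesised to fall from 72.6% to 36.3%. A missed tube could lower that composite if it was the patient's only component.

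**Working it through.** The plan states no figure for the PEG endpoint, so there is none to reproduce. The check covers when PEG is first recorded, how much one patient weighs, and what the background PEG rates would imply.

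**1. Time from RT Day 1 to the first scheduled PEG record.** Inputs: 21 fractions in Arms 1 and 2 and 30 in Arm 3 (Section 5.5), and a first visit at 6 weeks ± 1 week, that is 35 to 49 days after RT ends (Section 5.6). Assume a Monday start, weekday treatment and no delays.

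| Course | RT ends, days after Day 1 | First PEG record, days after Day 1 |
|---|---|---|
| Arms 1–2, one twice-daily treatment in the course (5.5) | 25 | 25 + 35 = 60 to 25 + 49 = 74 |
| Arms 1–2, once daily throughout (allowed by 5.5) | 28 | 28 + 35 = 63 to 28 + 49 = 77 |
| Arms 1–2, one twice-daily treatment each week (14.1, footnote 6) | about 22 | about 57 to 71 |
| Arm 3 | 39 | 39 + 35 = 74 to 39 + 49 = 88 |

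For Arms 1 and 2 the range is 57 to 77 days: 57/7 = 8.1 weeks to 77/7 = 11.0 weeks. Section 7.2 allows RT delays, which would lengthen it.

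**2. Weight of one misclassified patient.** The shift is 1/n.

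- Arm 1 at the target of 20: 1/20 = 5.0 points.
- Arm 1 at the 13 enrolled by December 2019 (Section 10.2): 1/13 = 7.7 points.
- All enrolled: 1/40 = 2.5 points, or 1/60 = 1.7 points if 20 more patients join.

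No shift is given for Arms 2 and 3. Section 10.2 planned 14 + 6 = 20 patients there, but 40 − 13 = 27 had already been enrolled outside Arm 1, and the split is not stated.

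**3. Scale.** Section 1.4 gives PEG rates of 6% without and 41% with primary-bed radiation. Assume these carry over to 20 Arm 1 patients:

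- 0.06 × 20 = 1.2, about 1 patient: 1/20 = 5%, exact 95% CI 0.1% to 24.9%.
- 0.41 × 20 = 8.2, about 8 patients: 8/20 = 40%, exact 95% CI 19.1% to 63.9%.

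The undercount from removed tubes is then 0 to 1 patient if PEG is rare and 0 to 8 if it is common. The documents give no removal times. Varying the share of the 8 tubes removed before the 6-week visit, purely as an assumption:

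| Share removed | Counted in use | Exact 95% CI |
|---|---|---|
| 0% | 8/20 = 40% | 19% to 64% |
| 25% | 6/20 = 30% | 12% to 54% |
| 50% | 4/20 = 20% | 6% to 44% |
| 75% | 2/20 = 10% | 1% to 32% |

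The number of tubes placed before RT is not given either, so the error in the other direction cannot be bounded.

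**The case against.** **The data may exist.** The PEG Form's fields are not in the documents. The Narcotics Form shares its submission schedule, yet narcotic use is documented from Day 1, so a form first due at 6 weeks can cover earlier events. A PEG is a procedure and is normally dated in the chart. This stands, and it is why the conclusion is conditional. The other possible sources are weaker. The Toxicity Form is continuous, but Section 9.4 excludes surgery-related events. The PSS-HN has a tube-fed level, but it is optional and not specific to PEG. Neither is named as the source for this endpoint.

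**A window exists.** A reader might infer that the plan has no counting period at all. That goes too far. Section 5.7 evaluates toxicity from the first RT dose until five years after treatment, and Section 9.4 tracks adverse events through the 6-week visit. But these are two different periods and neither is tied to PEG. The 6-week phrase in the Section 1.9 composite reads as belonging to narcotics.

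**The population.** The wording about all enrolled patients could be read as conflicting with the treated-patient rule in 5.7. In context it plausibly means all three arms, in contrast to the neighbouring endpoints limited to Arm 1. It needs a clarifying word and is not a contradiction.

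**Late tubes.** It is tempting to call a tube placed long after RT a miscount. Section 1.3 lists swallowing difficulty as a chronic effect, so a late tube may be real toxicity. It should be shown separately rather than dropped.

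**Conclusion.** The point holds in a limited form. The stated endpoint is placement; the stated schedule measures use from about 8 to 11 weeks after RT Day 1 in Arms 1 and 2. Followed literally, it can miss temporary tubes and cannot separate tubes placed before RT from those placed because of it. This is more than a missing definition, because the two quantities differ.

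The size of the error cannot be derived and may be zero. Each misclassified Arm 1 patient is worth 5.0 points at 20 patients and 7.7 at 13. Its direction is not known.

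Two stronger readings are not supported. A reader might infer from the table above that an apparent halving of PEG use would be an artefact. The removal shares are hypothetical and the 41% rate is borrowed from another cohort, so the table shows what could happen and is not evidence that it does. A reader might also infer that the trial's conclusion is at risk. The sample size rests on weight loss alone, PEG is reported as a proportion with a confidence interval, and 10.4.4 sets out no test of PEG or of the composite. What is affected is the interpretation of one secondary toxicity result.

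**What to change.** 1. Add PEG status to calendar 14.1 at Days 1, 22 and 36, beside the narcotic row.
2. Record placement and removal dates on the PEG Form. For patients already treated, take them from the chart. If the form already holds both dates, this step is done.
3. In 10.4.4, define the endpoint as new PEG placements from RT Day 1 through the 6-week post-treatment visit, among patients who started RT, reported by arm with a 95% CI. Show separately the tubes already in place on Day 1, and the placements after the 6-week visit within the five-year toxicity period of Section 5.7.

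The cost is one calendar row on existing visits, two date fields, one definition, and a chart check for patients already treated. The downside is a little extra data entry and chart review. No new visit, test or patient is needed.

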5.6 Follow-Up Assessments after Adjuvant Therapy

Follow-up assessments will be planned at the following time points; actual follow up times may vary due to patient logistics and compliance:

- 6 weeks (+/- 1 week) following completion of adjuvant therapy
- 4 months (+/- 2 weeks) following completion of adjuvant therapy
- 6, 12, 18, 24, 30, 36, 48, and 60 months (+/- 6 weeks) following completion of adjuvant therapy
- annually thereafter for 5 years (total follow-up 10 years)

Patients with disease progression will only be followed for survival and will not stay on the above follow-up schedule. Their follow-up schedules will then be at the discretion of the investigator.

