10.0 STATISTICAL CONSIDERATIONS

10.1 Study Design

This is a three-arm non-randomized Phase II trial. All the enrolled patients will undergo resection of the primary tumor site and involved/at risk regional neck nodes. Patients will be assigned to one of three adjuvant treatments based on the clinical and pathologic staging and the details of the pathology report. 90%, 5%, and 5% of the patients are expected to be in Arm 1, 2, and 3, respectively. The overarching goal is to reduce treatment-related toxicity while maintaining efficacy. Weight loss is a reliable, easily measured and practical surrogate marker of mucosal toxicity. Therefore, the primary objective is to determine the percent weight loss of patients during POAmCRT in Arm 1. The secondary objectives are to evaluate the proportion of PEG tube placements, determine the serum creatinine changes in patients receiving POAmCRT, evaluate the narcotics administration of patients 6 weeks after POAmCRT, document the measures of Quality of Life (QOL) at baseline/during treatment/one year after completion of treatment on all arms, determine the disease recurrence free survival (RFS) at 24 months post-treatment in each arm, and determine progression free survival (PFS) and overall survival (OS).

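### Arm 1's 24-month recurrence rate is planned as a crude binomial proportion with no rule for incomplete follow-up or death without recurrence; a censored estimate would be less biased at the cost of wording only (minor)

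*Combined protocol and SAP*

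**What the plan says.** - **Estimator.** Section 10.4.4 on DRR-24: "The proportion and 95% CI from binomial distribution will be shown for Arm 1". It does not name the interval method.
- **Labels.** The same section continues: "If 95% upper CI is smaller than 20%, then the risk of disease recurrence is deemed as acceptable". A lower limit above 20% earns 'unacceptable'. It then says that no hypothesis about DRR-24 is tested and that the result is preliminary. It gives no reading for an interval that spans 20%.
- **Time-to-event methods.** Kaplan-Meier is named for PFS and OS only, and "PFS will be calculated from the date of surgery to the date of progression, death of any cause, or last known date alive".
- **Who counts.** Section 5.7: "All patients who undergo surgery are evaluable for disease relapse".
- **Follow-up.** Section 5.6 schedules visits at "6, 12, 18, 24, 30, 36, 48, and 60 months (+/- 6 weeks) following completion of adjuvant therapy" and warns that "actual follow up times may vary due to patient logistics and compliance". Section 5.10 keeps patients who stop treatment early in follow-up.
- **Endpoint name.** Section 2.2: "To determine the disease recurrence rate at 24 months post-treatment in each arm". Section 10.1: "determine the disease recurrence free survival (RFS) at 24 months post-treatment in each arm". Section 10.4.4 uses both terms and does not define RFS.

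**The concern.** A fixed-time binomial proportion needs every patient's status at 24 months. The plan expects irregular follow-up but has no rule for a patient whose status is unknown, or who dies free of recurrence. Section 5.7 says who is evaluable, which most naturally puts all operated Arm 1 patients in the denominator. It does not say how to score someone last seen clear at month 9. Section 5.10 concerns continued follow-up, not analysis.

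PFS does not fill the gap. It starts at surgery, counts deaths, and runs to the last date known alive instead of the last disease assessment. The two endpoint names add to the ambiguity: a death without recurrence is an event for RFS as usually defined, but not for a recurrence rate.

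DRR-24 is the one efficacy measure with a stated limit. Section 1.8 accepts de-intensified treatment only if relapse does not increase, and Section 1.9 sets the 20% ceiling. A counting rule chosen after the data are seen could affect which label is reported.

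**Working it through.** **Inputs from the documents.** Threshold 20% at 24 months (Section 1.9). Historical recurrence 10%, of which 89% by 24 months (Section 1.9): 0.10 × 0.89 = 8.9%. Section 10.2 had 13 patients in Arm 1 and allows up to 7 more, so 13 to 20. The plan gives no precision figure for DRR-24. Its only drop-out figure is 15%, used to size the weight endpoint: 20/0.85 = 23.5, rounded up to 24, which reproduces.

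**Assumptions.** Loss by 24 months L = 5%, 10% or 15%; constant recurrence hazard; loss times uniform over 0 to 24 months and unrelated to recurrence; exact (Clopper-Pearson) intervals.

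**1. Bias of the crude proportion.** For true 24-month rate p, the chance that a patient due to be lost recurs first is E = 1 − p/[−ln(1−p)].
- Losses scored recurrence-free: R1 = (1−L)p + L·E.
- Losses dropped: R2 = R1/[(1−L) + L·E].

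For p = 20%, E = 1 − 0.2/0.2231 = 0.1037. At L = 15%, R1 = 0.170 + 0.0156 = 18.6% and R2 = 0.1856/0.8656 = 21.4%.

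| True rate | Loss | Scored recurrence-free | Dropped |
|---|---|---|---|
| 20% | 5% | 19.5% | 20.4% |
| 20% | 10% | 19.0% | 20.9% |
| 20% | 15% | 18.6% | 21.4% |
| 8.9% | 15% | 8.2% | 9.6% |

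For scale, the exact interval for 2/20 is 1.2% to 31.7%.

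**2. Where the labels fall.** With x = 0 the upper limit is 1 − 0.025^(1/n): 16.8% at n = 20, 17.6% at 19, 18.5% at 18, 19.5% at 17 and 20.6% at 16. One recurrence in 20 gives 24.9%. So at 17 to 20 patients 'acceptable' needs zero recurrences, and at 16 or fewer it cannot be reached. 'Unacceptable' starts at 9/20 (lower limit 23.1%; 8/20 gives 19.1%).

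**3. How often the two rules disagree.** Each patient is a recurrence (probability R1), lost with unknown status (L(1−E)) or followed and clear. I summed the trinomial probabilities of all outcomes in which x/n and x/(n − lost) carry different labels, at a true 8.9%:

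| n | 5% loss | 10% loss | 15% loss |
|---|---|---|---|
| 20 | 0.3% | 2.5% | 7% |
| 18 | 5% | 12% | 17% |

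Most of this is the zero-recurrence case: 'acceptable' goes once 4 of 20, or 2 of 18, are dropped. Every change is between a label and no label.

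**4. If Section 5.7 rules out dropping.** The open choice is then event versus non-event. With no known recurrences and one unresolved patient, 0/20 (upper limit 16.8%) is 'acceptable' and 1/20 (24.9%) has no label. One death without recurrence does the same, depending on whether the endpoint is read as a recurrence rate or as RFS.

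**The case against.** **The plan already limits the consequence.** DRR-24 is secondary, declared untested and offered as preliminary, and the sample size rests on weight loss alone. Kaplan-Meier PFS gives a partial cross-check. All of this stands and is why the point is minor.

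**Section 5.7 may forbid dropping patients.** On its natural reading it does, and the disagreement rates in step 3 then fall away. The low bias of the crude rate and the event versus non-event question remain.

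**The 15% loss is borrowed.** It was set for a weight endpoint of about four weeks, not for 24-month follow-up. That is fair, so the range is shown; at 20 patients and 5% loss the two rules almost never disagree.

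**A reader might infer that one lost patient commonly decides the result.** Examples exist: 0/17 against 0/16, and 8/20 (lower limit 19.1%) against 8/19 (20.3%). But comparing recurrence-free scoring with dropping, no single loss changes the label at 18 or 19 patients. At 20 patients and a true 8.9% the chance is practically zero; only at 17 does it reach 4% to 8%. The 8/20 case needs an observed 40% recurrence against a historical 10%.

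**Censoring does not remove the sensitivity at zero recurrences.** That is correct: the denominator still matters there. The gain is that it is fixed in advance.

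**Conclusion.** The point holds as a minor one. The stated estimator is crude where follow-up may be incomplete, and the counting rule is missing. At an assumed 5% to 15% loss, a true 20% is misread by about 0.5 to 1.4 points in either direction, well inside the interval width. The choice can add or remove a label, most plausibly with zero recurrences and 17 to 20 patients, but cannot turn 'acceptable' into 'unacceptable'. These figures rest on the assumed loss range, a constant hazard, losses unrelated to recurrence, and exact intervals; another interval method moves the cut-offs.

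Two stronger inferences are not supported. The rule does not readily give false reassurance: at 20 patients a true 20% is cleared with probability 0.8^20 = 1.2% under full follow-up, and (1 − 0.1856)^20 = 1.6% if 15% are lost and scored recurrence-free. And the fact that most trials of this size would end with no label reflects the sample size, not the handling of losses.

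**What to change.** In Section 10.4.4:
1. Estimate DRR-24 from completion of therapy as the 24-month cumulative incidence of recurrence, with death without recurrence as a competing event. State the time origin for an Arm 1 patient who does not complete radiotherapy.
2. Censor recurrence-free patients at their last disease assessment. Treat the 24-month visit, with its six-week window, as month 24, so that a recurrence found there counts and a patient clear there counts as followed.
3. Report the number followed to 24 months and a 95% interval by a method named in advance. With no recurrences the usual variance is zero, so give an exact binomial limit on a pre-stated denominator.
4. Call the two labels descriptive, and say that an interval spanning 20% is inconclusive.

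Use one endpoint name in Sections 2.2, 10.1 and 10.4.4.

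**Cost.** Wording only. The interval is slightly wider: 20 patients with recurrences at months 6 and 12 and losses at months 3, 9 and 15 give a crude 10.0% (exact 1.2% to 31.7%). The censored estimate is 1 − (18/19)(16/17) = 10.8% (complementary log-log 2.8% to 36.9%); with no competing deaths, cumulative incidence and Kaplan-Meier coincide. The cut-offs can also shift: with complementary log-log, 'unacceptable' starts at 8/20 (lower limit 22.4%) instead of 9/20, which a true 20% reaches 3.2% instead of 1.0% of the time. The method should be chosen with that in view.

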Patients (and clinicians) will not accept an increased risk of disease recurrence even with a significant reduction in toxicity with de-intensified therapy.²¹ To address this concern, we will establish rates of disease recurrence for Arm 1 that will be unacceptable. Our historical control data showed that the absolute risk of disease recurrence in patients with the characteristics of Arm 1 was 10% and that 89% of these recurrence events occurred by 24 months after completion of therapy. The upper threshold for disease recurrence in Arm 1 will be 20% by 24 months after completion of therapy. In Arms 2 and 3, we will report the proportion of patients with disease recurrence, but will not develop formal hypotheses testing because Arm 2 patients will be too few in number and Arm 3 patients will receive standard POACRT.

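### Does the 20% recurrence rule for Arm 1 need rewriting because it will seldom give a verdict and the plan says recurrence is not tested?

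*Combined protocol and SAP*

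**What the plan says.** Section 1.9 argues that neither patients nor clinicians would trade more recurrence for less toxicity. It continues: "To address this concern, we will establish rates of disease recurrence for Arm 1 that will be unacceptable". The figure follows: "The upper threshold for disease recurrence in Arm 1 will be 20% by 24 months after completion of therapy". The historical recurrence risk for comparable patients is given as 10%, and "89% of these recurrence events occurred by 24 months after completion of therapy". Section 1.9 also says that recurrence in Arms 2 and 3 will not be formally tested. It does not say whether recurrence in Arm 1 will be.

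Section 10.4.4 gives the analysis: "The proportion and 95% CI from binomial distribution will be shown for Arm 1". Two rules follow. The first is "If 95% upper CI is smaller than 20%, then the risk of disease recurrence is deemed as acceptable". The second is "If 95% lower CI is larger than 20%, then the risk of disease recurrence is deemed as unacceptable". The paragraph closes with a qualification: "Given our small sample size, there are some uncertainties", and for that reason "we do not test the hypothesis about (DRR-24) but provide a preliminary data for planning future studies".

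Section 10.2 bases the sample size on weight loss alone. It gives 20 patients for 80% power and 24 to be enrolled in Arm 1. Its later update has 13 enrolled against a target of 20, and an extension that ends at 7 more Arm 1 patients or 20 more patients in any arm, whichever comes first.

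**The concern.** Three things look wrong on a first reading.

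- **Status of the threshold.** Section 1.9 offers 20% as the safeguard for Arm 1 and waives testing only for the other two arms. Section 10.4.4 turns it into a rule that works like a two-sided test against 20%, and then says there is no test.
- **Yield.** With about 20 patients the rule can rarely give either label, and nothing is said about an interval that contains 20%.
- **Interval method.** The method is not named. The only related reference (number 23, cited for the PEG and narcotics proportions) compares seven methods, so a borderline label could depend on a choice made after the data are seen.

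At stake is what may be concluded about recurrence in a trial whose case for giving less treatment depends on recurrence not rising.

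**Working it through.** **Inputs.** Threshold 20% at 24 months and historical risk 10% with 89% of events by 24 months (section 1.9), so 0.89 × 10% = 8.9% at 24 months. Arm 1 target n = 20 (section 10.2). Two-sided 95% binomial interval (section 10.4.4).

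**The plan's own figure.** For weight loss, the standardised difference is (7.39 − 3.7)/5.46 = 0.676. A two-sided one-sample t test at 5% has 81.8% power at n = 20 and 79.6% at n = 19, so 20 is correct. Allowing for drop-out, 20/(1 − 0.15) = 23.5, rounded up to 24. Both figures reproduce. The plan states no power for recurrence.

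**Counts that earn a label at n = 20.** The exact (Clopper-Pearson) upper limit for 0/n is 1 − 0.025^(1/n). At n = 20 this is 16.8%.

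| Interval | *Acceptable* (upper limit < 20%) | *Unacceptable* (lower limit > 20%) |
|---|---|---|
| Exact | 0 (16.8%); 1/20 gives 24.9% | ≥ 9 (23.1%); 8/20 gives 19.1% |
| Wilson | 0 (16.1%); 1/20 gives 23.6% | ≥ 8 (21.9%) |
| Wald | ≤ 1 (14.6%); 2/20 gives 23.1% | ≥ 9 (23.2%); 8/20 gives 18.5% |

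**Probability of each label, exact limits, n = 20.** P(*acceptable*) = (1 − p)^20 and P(*unacceptable*) = P(X ≥ 9), with X binomial(20, p).

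| True rate p | *Acceptable* | *Unacceptable* | No label |
|---|---|---|---|
| 8.9% | 15.5% | 0.0% | 84.5% |
| 10% | 12.2% | 0.0% | 87.8% |
| 20% | 1.2% | 1.0% | 97.8% |
| 30% | 0.1% | 11.3% | 88.6% |
| 40% | 0.0% | 40.4% | 59.6% |
| 50% | 0.0% | 75% | 25% |

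The row at 20% is no defect. When the true rate equals the reference value, an interval with at least 95% coverage must contain it in at least 95% of trials. The rows at 10% and 30% show what 20 patients can tell about a rate 10 points from the threshold. The rule becomes more decisive as the true rate moves further away.

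**Effect of the interval method.** Exact and Wilson limits differ only at 8/20, which occurs in 11.4% of trials at a true 30% and 18.0% at 40%. They agree on *acceptable*. Wald differs from both at 1/20, which has probability 20 × 0.1 × 0.9^19 = 27.0% at a true 10%. Wald rests on a normal approximation and is the least natural reading of an interval taken from the binomial distribution.

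**Effect of Arm 1 size.** With exact limits, 0 events gives an upper limit of 20.6% at n = 16 and 19.5% at n = 17, so *acceptable* cannot be reached below 17 patients. If the observed share of 13/40 = 0.325 continues (an assumption), the extension brings Arm 1 to at least 17 with probability 93%, and to 20 with probability 49%. Across n = 17 to 20 the no-label share is 82% to 98% at true rates of 10% to 30%. Enrolling 24 would not change this: 92.0%, 98.3% and 84.7% at 10%, 20% and 30%.

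**The case for a change.** The best case for a change is that section 1.9 makes recurrence the condition on which de-intensification stands, and this rule is the only stated criterion for judging it. At the historical rate the trial would earn the *acceptable* label only 12% to 16% of the time. At three times that rate it would earn *unacceptable* 11% of the time. The disclaimer follows the labels without withdrawing them, so a reader may not know which governs. Naming the interval, calling other results inconclusive and aligning section 1.9 would cost only a few words.

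Some of this stands. The two sections are not fully aligned, the method could have been named, and the chance of *acceptable* at 10% is low.

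The rest does not lead to a change. That Arm 1 would be tested is inferred from the silence of section 1.9, which is background; section 10.4.4 is the operative text and says there is no test. The low yield is low power for an endpoint the trial was never sized on. Deleting the two rules would remove the only prespecified recurrence benchmark after 40 patients had been enrolled, which invites a worse criticism. Requiring exact limits instead of Wilson would lower the chance of *unacceptable* from 23% to 11% at a true 30%, so that choice is a trade-off and not a correction.

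**Conclusion.** No change is needed. Followed as written, the plan reports the Arm 1 proportion with a 95% binomial interval and attaches a label only when the interval lies wholly on one side of 20%. A result such as 2/20 (exact upper limit 31.7%) gets no label because the data do not settle the question, and an analyst would describe it as inconclusive without being told to. The missing method name is a gap that analysts fill sensibly: exact limits are the natural reading, and Wilson would change the label only at 8/20. Rewording section 1.9 would alter no result. No sample size, primary analysis or stopping decision depends on the labels, and the proportion, its interval, PFS and OS are reported whichever label applies.

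The 88% to 98% no-label figures assume exact limits, n = 20 and true rates of 10% to 30%. They describe the limits of a small secondary estimate, which section 10.4.4 openly calls preliminary.
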